5.4.2.2 Cycle B: Virtual Police Interaction Assessment

After the final VR intervention session, all participants will be assessed via a remote semi-structured interaction with a police or security officer avatar. Approximately 4weeks after the final VR intervention session, participants in Cycle B will be assessed once again via a remote interaction with a police or security officer. These interactions are specifically designed to serve as an index of behaviorally defined skills associated with effective interactions with a police officer. The police officer will be programmed with a semi-structured set of prompts to use when interacting with the participant, and will rate the participant's responses. The interaction is designed with guidance from law enforcement officers with particular experience working with individuals with intellectual and developmental disabilities. We will use video recordings of both the participant wearing the headset and behaviors while in the VR experience to code behaviors. These recordings will be coded for a set of both virtual and real-world behaviors that would

encourage successful police interactions (i.e. making appropriate eye contact, orienting to the virtual officer, etc.).

While it is important that our research participants are approached by simulated Police Officers, it is also critical that risks for stress/distress and other harms are minimized. To this end, the virtual reality Police Officer will take a casual, non-accusatory approach to questioning the participant, and will follow their standard procedures in the type of scenario where they need to inquire with an individual but where that individual is not a suspect.

Consistent with ethical standards in psychological research, all participants will be de-briefed immediately following the Remote Interaction Assessment. The research participant will be offered the opportunity to ask questions, and to provide their thoughts and feedback on the study procedures and practices. Research participants will also be asked to rate their experience with the remote Police Interaction, as well as the study process and procedures overall, in a formal questionnaire. Information gathered from both the interview and the questionnaire will be used to inform the researchers of how the practice is affecting research participants.

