6.2 Secondary Endpoints

Secondary endpoints will include the following:

- The changes in Police Interaction Knowledge Questionnaire Scores from Pre-Treatment to Post-Treatment for the Virtual Reality Intervention and BE SAFE Video-Based intervention or treatment-as-usual:
- The maintenance of learned skill improvements, indexed via the 4-week (Cycle B) Follow-Up administration of the Virtual Police Interaction Assessment.

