6.3.2 Efficacy Analysis

The primary analysis will be based on an intention to treat approach and will include all subjects randomized at Visit 1.

The primary efficacy endpoint will be the change in post-treatment Live Police Interaction Assessment Scores between the Virtual Reality Intervention and BE SAFE Video-Based intervention and the change in scores between the Baseline Assessment and Live Police Interaction Assessment. In the case of Cycle 2, the Baseline Assessment will be compared to the Virtual Police Interaction Assessment between the Virtual Reality Intervention and treatment-asusual groups. The study hypothesis is that participants randomly assigned to the Virtual Reality Intervention will perform better on the post-treatment Live or Virtual Police Interaction Assessment than will participants randomly assigned to the BE SAFE Video-Based intervention or treatment-as-usual condition.

The secondary endpoint will include changes in Police Interaction Knowledge Questionnaire Scores from Pre-Treatment to Post-Treatment for the Virtual Reality Intervention and BE SAFE Video-Based intervention or treatment-as-usual. The study hypothesis is that participants randomly assigned to the Virtual Reality Intervention will exhibit significantly greater improvement from Pre-Treatment to Post-Treatment on Police Interaction Knowledge Questionnaire than will participants randomly assigned to the BE SAFE Video-Based intervention condition or the treatment-as-usual condition. An additional Secondary endpoint is maintenance of learned skill improvements, indexed via the 4-week Follow-Up administration of the Virtual Police Interaction Assessment in Cycle B. The study hypothesis is that participants randomly assigned to the Virtual Reality Intervention will exhibit significantly greater Live Police Interaction Assessment Scores and skill improvement/maintenance 4-week follow-up than will participants randomly assigned to the treatment-as-usual condition.

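### Section 6.3.2 states the Cycle B 4-week maintenance hypothesis on the Live score, which Cycle B never collects, and does not fix which contrast tests maintenance

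*Combined protocol and SAP*

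**What the plan says.** Section 6.2 lists maintenance as a secondary endpoint, "indexed via the 4-week (Cycle B) Follow-Up administration of the Virtual Police Interaction Assessment". Section 6.3.2 gives the same definition: the endpoint is "indexed via the 4-week Follow-Up administration of the Virtual Police Interaction Assessment in Cycle B". The next sentence, which states the hypothesis, names a different instrument. It says that the VR arm "will exhibit significantly greater Live Police Interaction Assessment Scores and skill improvement/maintenance 4-week follow-up than will participants randomly assigned to the treatment-as-usual condition".

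Section 5.4.2 defines the two instruments. Under 5.4.2.1, headed for Cycle A, the Live assessment is an encounter with a real officer after the final session. Under 5.4.2.2, headed for Cycle B, the post-treatment assessment reads: "all participants will be assessed via a remote semi-structured interaction with a police or security officer avatar". For the 4-week visit the same section says "participants in Cycle B will be assessed once again via a remote interaction with a police or security officer", leaving out avatar.

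Section 4.4.1 confines the 4-week visit to Cycle B, and section 5.3.2 does the same for the treatment-as-usual arm. Section 6.4 describes one ANOVA comparing VR with video modeling on the Live data and another for the questionnaire. It names no analysis for the Virtual score or for week 4.

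**The concern.** An endpoint and its hypothesis should refer to the same measurement. Here the definition points to the Virtual assessment and the hypothesis to the Live one, in adjacent sentences of the analysis section. Read literally, the hypothesis concerns an outcome that no one will have.

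The second difficulty would remain if the label were corrected. The hypothesis asks for a greater score at 4 weeks and, in the same clause, for improvement or maintenance of skill. These are different contrasts and can disagree. If the plan does not say which one is the test, the choice can be made after the results are known, and a claim that the training lasts would then rest on whichever contrast came out favourably.

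**Working it through.** No figure in the plan is specific to this endpoint, so the check is a comparison of sections and a short piece of algebra. The one detectable effect in section 6.4 (d = 0.74) is not tied to the 4-week visit and plays no part.

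**Step 1. Which instrument exists where.**

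| | After the last session | 4 weeks later | Comparator |
|---|---|---|---|
| Cycle A | Live (5.4.2.1) | no visit (4.4.1) | video modeling (5.3.1) |
| Cycle B | Virtual (5.4.2.2) | Virtual (6.2 and the definition in 6.3.2) | treatment-as-usual (5.3.2) |

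The hypothesis needs Live scores, at 4 weeks, with a treatment-as-usual comparator. Live with 4 weeks gives 0 planned participants; Live with treatment-as-usual also gives 0. The endpoint as defined (Virtual, 4 weeks, Cycle B) has about 48 planned evaluable participants (sections 3.2.2 and 6.4). That would be 24 per arm under 1:1 allocation, a ratio the plan does not state.

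**Step 2. Is the 4-week officer an avatar?** The 4-week sentence alone does not say so. The rest of 5.4.2.2 does. Its heading is the Virtual assessment. It then covers both occasions together: "The police officer will be programmed with a semi-structured set of prompts to use when interacting with the participant". On scoring it says "We will use video recordings of both the participant wearing the headset and behaviors while in the VR experience to code behaviors". Later it calls the officers simulated and refers to the officer in virtual reality. Section 3.1.3 describes the follow-up as a repeat of the outcome measures, and Table 1 puts both Cycle B occasions on one row. All of this describes one instrument given twice.

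**Step 3. The two quantities in the hypothesis.** Let V3 and V4 be an arm's mean Virtual score at Visit 3 and at 4 weeks, C = V4 − V3 the change within an arm, and D the VR mean minus the treatment-as-usual mean. Then

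D4 = V4(VR) − V4(TAU) = [V3(VR) + C(VR)] − [V3(TAU) + C(TAU)] = D3 + [C(VR) − C(TAU)].

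- If D3 = g > 0 and C(VR) − C(TAU) = −g/2, then D4 = g/2 > 0. The VR arm is still ahead at 4 weeks although half its advantage has gone.
- If D3 = 0 and both changes are 0, then D4 = 0. The VR arm has kept its Visit 3 score and shows no advantage.

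A higher 4-week score and a maintained score can therefore lead to opposite conclusions.

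**Step 4. Does another section choose between them?** In 6.3.2, the Cycle B part of the primary endpoint compares the baseline and Virtual assessments between arms, but gives no model and does not mention week 4. Section 6.4 lists possible covariates (intake knowledge, sensory sensitivity, verbal ability, age); the baseline interaction score is not among them. Section 6.3.1 adds a baseline variable only where the arms differ significantly. Nothing settles the contrast.

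**The case against.** The strongest reply is that Live is a slip carried over from Cycle A and would mislead no one. The endpoint is defined twice as the Virtual assessment, once immediately before the hypothesis, and the comparator and visit named in the hypothesis exist only in Cycle B. A competent analyst would use the Virtual score. This largely stands: it makes the label error close to clerical. It does not remove the need to correct it, because no Cycle B model statement exists elsewhere to override the wrong word.

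A second reply is that change from Visit 3 to 4 weeks is an equally legitimate meaning of maintenance, so prescribing a between-arm 4-week comparison is a preference. It stands to this extent: the documents do not exclude that meaning, and the contrast recommended here is a choice. The need for some choice remains, since the plan makes none. The between-arm contrast has two advantages: it is the comparison with treatment-as-usual that the hypothesis states, and it rests on randomization, whereas change within the VR arm has no control.

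**Conclusion.** The point holds for the hypothesis and for its undefined test. As worded, the 4-week hypothesis in 6.3.2 refers to scores from 0 planned participants and contradicts the endpoint definition beside it and in 6.2. It also merges two contrasts without saying which decides.

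Two stronger readings should be resisted. A reader might infer that maintenance cannot be assessed at all; it can, because about 48 Virtual scores are planned for the endpoint as defined. A reader might also infer from the missing word in 5.4.2.2 that a human officer replaces the avatar at 4 weeks, so that the change from Visit 3 mixes two instruments. The text does not support this. Some wording is untidy: the programmed officer is said to rate responses, as the human officer does in 5.4.2.1, and the blinding paragraph in 9.1.2 mentions police officers without limiting them to Cycle A. Neither establishes a human officer at 4 weeks, so no instrument-change bias is claimed.

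The reach is one secondary endpoint. The primary endpoint, sample size and conduct are untouched by this point. The conclusion assumes that the avatar assessment is the intended 4-week measure; if the sponsor intended otherwise, 5.4.2.2, 6.2 and 6.3.2 would need to be reconciled.

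**What to change.** 1. In the maintenance hypothesis of 6.3.2, replace Live with Virtual.
2. In the same place, define one test: the between-arm difference (VR minus treatment-as-usual) in the 4-week Virtual score, adjusted for the baseline Virtual score that section 5.4.1.2 already collects, for example by ANCOVA. Report within-arm change from Visit 3 to 4 weeks descriptively.
3. In 5.4.2.2, add avatar to the 4-week sentence so that it matches the post-treatment one.

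Items 1 and 3 are single-word edits. Item 2 is slightly more, since it settles what the secondary endpoint estimates, and it should be in place before Cycle B outcomes are examined by arm. It assumes that baseline and follow-up recordings are coded on the same scale, which the plan should confirm. No extra data, visits or participants are needed.

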5.4.3 Police Knowledge Questionnaire

This questionnaire has been developed by the study team as a measure of knowledge of officer expectations for interaction and will be administered to all participants both pre-treatment and post-treatment, as well as during the follow-up visit for Cycle B.

5.4.4 Floreo Feedback Ouestionnaire

This questionnaire has been developed by the study team as a measure of how well the VR simulated a real police interaction and will be administered to all participants post treatment.

5.5 Video/Audio Recording

Virtual and in person clinical testing will be audio and video recorded in accordance with CHOP Policy RI-2-03 (Recording or Filming of Patients). Audio and video recordings may be used for clinical supervision, training, educational, or research purposes.

The VR sessions may be recorded for research, accuracy, and safety purposes. Video recording will not be mandatory; permission to record these sessions will be obtained in the consent form. The VR sessions will be recorded to capture any adverse effects of the VR, which may help prevent such effects in future visits. It would also be helpful to have a video record of the session to determine how the gyroscopic effects in the VR module correspond to the subjects' movements. Video modeling sessions may also be recorded for comparison purposes.

The Baseline Assessment as well as Virtual and Live Police Interactions will be recorded for research purposes. The interactions will be coded for a set of behaviors that would encourage successful police interactions (i.e. making appropriate eye-contact, orienting to the virtual officer, etc.). All recordings will be stored on a secure CHOP-approved server. If conducted via videoconference, they will be recorded through the CHOP- approved platform used.

5.6 Safety Evaluation

Immediately after completing each intervention session, research staff will ask subjects about any side effects experienced during the session. Research staff will also document the subject's overall perceived mood and emotional state.

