5.3.2 Cycle B: Treatment-as-usual

Subjects assigned to the control condition will not receive any training with PSM, but will engage with the software for their assessments, and will continue their other treatments as usual. Participants in the treatment-as-usual arm will be screened for subject health status in preparation for their sessions.

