5.4.1.2 Cycle B

Before beginning the first VR or video modeling intervention session, all participants will complete a baseline novel remote assessment of police interactions skills. These interactions are designed to measure each participant's ability to interact with a virtual police officer prior to completing either intervention. This assessment will include coded video recordings of participants wearing the VR headset while engaging in a standardized experience. The behaviors of the participant inside the virtual environment will also be coded. The interaction is designed with guidance from law enforcement officers with particular experience working with individuals with intellectual and developmental disabilities. The live interaction will be video-recorded via a CHOP-approved, HIPPA compliant videoconference platform. These recordings will be coded for a set of behaviors that would encourage successful police interactions (i.e.: making appropriate eye contact, etc.)

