8 SAFETY MANAGEMENT

8.1 Clinical Adverse Events

Clinical adverse events (AEs) will be monitored throughout the study. The PI and the research team will work together to minimize minor adverse events. This will be accomplished through systematic assessment for adverse events through active clinical observation and post-session

questionnaires. If adverse events occur, we will solicit direct guidance and feedback from CHOP's IRB, and immediately implement safeguards to decrease or eliminate future risks. Minor AEs that are unrelated to study participation will be reported to CHOP's IRB and the NIH program officer in a quarterly report.

Safety research on Virtual Reality (VR) indicates that photosensitive seizures, headache, and vertigo are adverse events possibly related to VR use. Our study team will consider new onset seizure disorder, any seizure triggered during participation, and either headache or vertigo severe enough to result in an emergency room evaluation or hospitalization to be SAEs and respond accordingly.

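### Section 5.6 ties its side-effect question to intervention sessions, which Cycle B treatment-as-usual subjects do not have, although both Cycle B arms wear the headset at three assessments

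*Combined protocol and SAP*

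**What the plan says.** Section 5.6 sets the rule for asking about side effects: "Immediately after completing each intervention session, research staff will ask subjects about any side effects experienced during the session". Both the trigger (an intervention session) and the period covered (that session) are stated.

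Under section 5.3.2, Cycle B TAU subjects "will not receive any training with PSM, but will engage with the software for their assessments". The assessments involve the headset:

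- **Baseline (5.4.1.2), before any intervention session.** "This assessment will include coded video recordings of participants wearing the VR headset while engaging in a standardized experience".
- **Visit 3 (5.4.2.2).** "After the final VR intervention session, all participants will be assessed via a remote semi-structured interaction with a police or security officer avatar". On scoring, the section says: "We will use video recordings of both the participant wearing the headset and behaviors while in the VR experience to code behaviors".
- **4 weeks.** Section 3.1.3 has the outcome measures given again to all Cycle B participants, and section 6.2 names the instrument as the Virtual Police Interaction Assessment.

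Section 8.1 has AEs monitored for the whole study and describes "systematic assessment for adverse events through active clinical observation and post-session" questionnaires. Section 6.3.3 puts everyone entered at Visit 1 in the safety analysis, tabulates AEs by type, body system, severity and relationship to intervention type, and gives incidences with exact 95% intervals.

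**The concern.** Spontaneous reporting usually yields fewer minor events than direct questioning. If staff follow section 5.6 as written, each Cycle B VR subject is asked three times and each TAU subject never, although TAU subjects also use the headset. The same symptom, such as nausea or headache after an assessment, would then be more likely to be recorded in one arm than in the other.

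A satisfactory safety profile is part of the overall objective in section 2, and sections 8.1 and 9.4.2 name seizure, headache, vertigo, nausea and eye strain as possible effects of VR. Baseline is each Cycle B subject's first headset exposure in the study, and no question is stated to follow it in either arm. Symptoms not asked about at the time cannot be reliably recovered later.

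**Working it through.** The plan gives no figure for this point, so there is none to reproduce. The check counts headset uses against stated questions.

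**Inputs**

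- VR-arm intervention sessions: 3 (section 5.2). TAU: 0 (section 5.3.2).
- Headset assessments in Cycle B, both arms: 3 (baseline, Visit 3, 4 weeks).
- Subjects per cycle: 48 (section 6.4). Assumed 1:1, so 48 / 2 = 24 per arm, all attending.

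**Count, section 5.6 read literally**

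| | TAU | VR |
|---|---|---|
| Headset uses per subject | 3 | 3 + 3 = 6 |
| Followed by the 5.6 question | 0 | 3 |
| Uses per arm | 3 × 24 = 72 | 6 × 24 = 144 |
| Asked per arm | 0 | 3 × 24 = 72 |
| No stated question | 72 | 144 − 72 = 72 |

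The total without a stated question is 72 + 72 = 144. In the VR arm these are the baseline use (before the first session), the Visit 3 assessment (after the last session) and the 4-week assessment. If the question followed every headset use, coverage would be 3 of 3 and 6 of 6 per subject.

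**Do other provisions supply the question?**

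- Section 8.1: its post-session questionnaires are not tied to named visits. Sections 4.3 and 4.4.1 and the measures in 5.1 list no side-effect form, and Table 1 has only a generic questionnaire row.
- Sections 5.4.2.2 and 4.4.1: a debrief follows the Visit 3 and 4-week assessments, with feedback and a rating of the experience. No side-effect item is named.
- Section 9.4.1: a debrief after each session, again with no side-effect item named.
- Section 9.4.2: subjects are asked how they feel between VR trials, and about specific symptoms if signs are seen. The routine check is tied to trials, not assessments.

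**What unequal questioning could do to the summary**

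With 0 recorded events in 24 TAU subjects, the exact upper limit is 1 − 0.025^(1/24) = 14.2%, so the interval is 0% to 14.2%. With 4 of 24 it is 4.7% to 37.4%.

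As an illustration with every rate assumed, give both arms the same true per-subject risk q, with capture of 90% in VR and r in TAU. Expected recorded cases are 24 × q × 0.9 and 24 × q × r. At q = 20% and r = 25% these are 4.3 and 1.2. Over q = 10% to 30% and r = 0% to 50%, VR runs from 2.2 to 6.5 and TAU from 0 to 3.6. The gap comes from ascertainment alone.

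**The case against.** The strongest reply is that section 5.6 does not stand alone. Section 8.1 covers the whole study, is not limited to one arm, and says post-session rather than post-intervention-session. The plan uses the word session loosely: section 3.1.3 gives subjects in each condition three of them, section 3.2.1 counts up to four virtual sessions in Cycle B, Table 1 marks VR sessions at all four Cycle B visits without separating arms, and section 5.3.2 says "Participants in the treatment-as-usual arm will be screened for subject health status in preparation for their sessions". On that reading the questionnaires could reach every assessment in both arms. This stands as far as it goes. A reader might infer from 5.6 that side effects at assessments would never be asked about, and the documents do not support that. They also do not state that the question will be asked.

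Three other strong readings should be set aside:

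- **That staff cannot see remote subjects.** Assessments are video-recorded with the subject wearing the headset (5.4.1.2, 5.4.2.2, 5.5). Staff are not in the room, but the subject is on camera.
- **That a planned between-arm safety test is biased.** Section 6.3.3 is descriptive and specifies no contrast or test. The risk lies in how the summaries are read.
- **That Cycle A has the same imbalance.** Both Cycle A arms have intervention sessions, and baseline and outcome there are live interactions.

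The study is classed as minimal risk and no efficacy result depends on this point. That limits its weight but does not remove the ambiguity.

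**Conclusion.** The concern holds as an unequal rule in section 5.6 that no other section clearly corrects. Followed literally, it reaches 0 of 72 TAU headset uses and 72 of 144 VR-arm uses in Cycle B. These counts assume 1:1 allocation, 24 per arm and full attendance. The safety set is everyone entered at Visit 1, so actual numbers may differ.

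The Cycle B AE incidences could differ between arms through ascertainment alone. The VR arm also has twice the headset uses (6 against 3 per subject), so a genuine exposure effect and a questioning effect could not be separated. The documents do not show that events would in fact be missed, or how many. This is worth changing because the correction is cheap and must be made before the data are collected.

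**What to change.** Reconcile section 5.6 with section 8.1. In 5.6, keep the existing question after each intervention session in both cycles and add, for example: *In Cycle B, the same scripted side-effect question and mood rating will also be completed after every other use of the headset, including the baseline, Visit 3 and 4-week assessments, identically in both arms.* In section 8.1, say which visits the post-session questionnaires cover and whether they are this same instrument. Add the item to sections 4.3 and 4.4.1 and to Table 1.

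This changes data collection only. It costs about a minute per visit (an estimate) for staff already on the call. More minor events will be recorded, mainly in the TAU arm.
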